3.8 INTERIM ANALYSES

No formal interim analysis for efficacy or safety is planned for this study.

4 SAMPLE SIZE DETERMINATION

A total sample size of 580 participants (randomization ratio 1:1, ie, 290 per intervention group) will be determined to demonstrate noninferiority of iGlarLixi versus IDegAsp in HbA1c reduction at Week 24 with 90% power and 2-sided significance level of 0.05 based on the following assumptions on the primary endpoint:

- True mean difference of zero between iGlarLixi and IDegAsp
- Common standard deviation of 1.05%
- Non-inferiority margin on the mean difference of 0.3%
- Dropout rate of 10%

Calculations were made based on two sample t-test using SAS® (Version 9.4).

5 SUPPORTING DOCUMENTATION

5.1 APPENDIX 1 LIST OF ABBREVIATIONS

AE:	adverse event
AESIs:	adverse events of special interest
BMI:	body mass index
ECG:	electrocardiogram
HGLT:	high level group term
HLT:	high level term
ITT:	intent-to-treat
LLT:	lower-level term
MAR:	missing at random
MedDRA:	medical dictionary for regulatory activities
MMRM:	mixed-effect model with repeated measures
OAD:	oral antidiabetic drug
PCSA:	potentially clinically significant abnormality
PT:	preferred term
SAE:	serious adverse event
SAP:	statistical analysis plan
SD:	standard deviation
SGLT-2:	sodium-glucose co-transporter 2
SOC:	system organ class
TEAE:	treatment-emergent adverse event
WHO-DD:	World Health Organization-drug dictionary

5.2 APPENDIX 2 PARTICIPANT DISPOSITIONS

The number (%) of participants included in each of the analysis populations listed in [Table 3](#) will be summarized.

Screen failures are defined as participants who consent to participate in the study but are not subsequently randomized. The number (%) of screen failures and reasons for screen failures will be provided in the screened population.

The number (%) of participants in the following categories will be provided:

- Randomized participants
- Randomized but not exposed participants
- Randomized and exposed participants
- Participants who completed the study treatment period as per protocol

- Participants who did not complete the study treatment period as per protocol and main reason for permanent intervention discontinuation
- Participants who completed the study period as per protocol
- Participants who did not complete the study period as per protocol and main reason for study discontinuation.

The number of exposed and not randomized participants will also be summarized.

Kaplan-Meier (KM) plots of the cumulative incidence of IMP discontinuation due to any reason or due to AE will be provided. Time to treatment discontinuation is defined as the number of days from the first dose of IMP until the day of treatment discontinuation. All completers are considered as censored observations. The censoring time is the number of days from the first dose of IMP until the last dosing date.

Protocol deviations

Critical and major protocol deviations (automatic or manual) will be summarized in the randomized population.

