7.2 PARTICIPANT DISCONTINUATION/WITHDRAWAL FROM THE STUDY

- A participant may withdraw from the study at any time at his/her own request or may be withdrawn at any time at the discretion of the Investigator for safety, behavioral, or compliance reasons. This is expected to be uncommon.
- At the time of discontinuing from the study, if possible, an early discontinuation visit should be conducted, as shown in the SoA. See SoA for data to be collected at the time of study discontinuation and follow-up and for any further evaluations that need to be completed.
- If the participant withdraws consent for disclosure of future information, the Sponsor may retain and continue to use any data collected before such a withdrawal of consent.
- If a participant withdraws from the study, he/she may request destruction of any samples taken and not tested, and the Investigator must document this in the site study records.

If participants no longer wish to take the IMP, they will be encouraged to remain in the study.

The Investigators should discuss with them key visits to attend. The value of all their study data collected during their continued involvement will be emphasized as important to the public health value of the study.

Participants who withdraw from the study intervention should be explicitly asked about the contribution of possible AEs to their decision, and any AE information elicited must be documented. All study withdrawals should be recorded by the Investigator in the appropriate screens of the e-CRF and in the participant's medical records. In the medical record, at least the date of the withdrawal and the reason should be documented.

In addition, a participant may withdraw his/her consent to stop participating in the study. Withdrawal of consent for intervention should be distinguished from withdrawal of consent for follow-up visits and from withdrawal of consent for non-participant contact follow-up, eg, medical record checks. The site should document any case of withdrawal of consent.

Participants who have withdrawn from the study cannot be rerandomized/reallocated (treated) in the study. Their inclusion and intervention numbers must not be reused.

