3.6 SAFETY ANALYSES

All safety analyses will be performed on the safety population as defined in [Section 2](#), unless otherwise specified, using the following common rules:

- The analysis of the safety variables will be essentially descriptive, and no testing is planned.
- Safety data in participants who do not belong to the safety population (eg, exposed but not randomized) will be provided.

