^b The table of all TEAEs presented by primary SOC and PT will define the presentation order for all other tables (eg, treatment-emergent SAE) presented by SOC and PT, unless otherwise specified.

Analysis of all adverse events

The overview of TEAE with the details below will be generated:

- Any TEAE
- Any treatment-emergent SAE
- Any TEAE leading to death
- Any TEAE leading to permanent treatment discontinuation

The AE summaries of **Table 5** will be generated with number (%) of participants experiencing at least one event.

Table 5 - Analyses of adverse events

Type of AE	MedDRA levels
All TEAE	Primary SOC, HLGT, HLT and PT
	Primary SOC and PT
	Primary and secondary SOC, HLGT, HLT and PT
Common TEAE ($\geq 1\%$ in any group)	Primary SOC and PT
TEAE related to IMP as per Investigator's judgment	Primary SOC and PT
TEAE by maximal intensity	Primary SOC and PT
Treatment emergent SAE	Primary SOC, HLGT, HLT and PT
	Primary SOC and PT
Treatment emergent SAE related to IMP as per Investigator's judgment	Primary SOC, HLGT, HLT and PT
TEAE leading to permanent treatment discontinuation	Primary SOC, HLGT, HLT and PT
	Primary SOC and PT
TEAE leading to death ^a	Primary SOC, HLGT, HLT and PT
	Primary SOC and PT
Pretreatment AE	Primary SOC and PT
Post-treatment AE	Primary SOC and PT
Post-treatment SAE	Primary SOC and PT

^a Death as an outcome of the AE as reported by the Investigator in the AE page

Among all TEAEs, Kaplan-Meier curves will be provided, when appropriate, for the time to first onset of the following PTs: nausea, vomiting and diarrhea as appropriate.

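### The SAP does not say how participants who stop IMP for a non-AE reason enter the Kaplan-Meier curve for AE discontinuation; if they are censored, the curve slightly overstates the cumulative incidence it claims to show

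*SAP*

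**What the plan says.** The plot is specified in SAP 5.2 (Appendix 2, participant dispositions): "Kaplan-Meier (KM) plots of the cumulative incidence of IMP discontinuation due to any reason or due to AE will be provided". The same rules serve both curves:

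- Time variable: "Time to treatment discontinuation is defined as the number of days from the first dose of IMP until the day of treatment discontinuation".
- Who is censored: "All completers are considered as censored observations".
- When: "The censoring time is the number of days from the first dose of IMP until the last dosing date".

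No competing-risks estimator is named, and nothing is said about non-AE stops in the AE curve.

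Two other displays cover the same event as simple counts and percentages. The disposition table in SAP 5.2 has a row for "Participants who did not complete the study treatment period as per protocol and main reason for permanent intervention discontinuation". SAP 3.6.2, Table 5, summarises "TEAE leading to permanent treatment discontinuation".

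Stopping for reasons other than an AE is foreseen. Protocol 7.2 says: "If participants no longer wish to take the IMP, they will be encouraged to remain in the study".

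**The concern.** For discontinuation due to any reason the rules are complete: every treated participant either stops (an event) or completes (censored). For discontinuation due to an AE there is a third group, those who stop for another reason. They are neither events nor completers.

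A participant who has permanently stopped IMP can no longer stop it because of an AE, so a non-AE stop is a competing event. Kaplan-Meier with those participants censored estimates how many would stop for an AE if no other reason for stopping existed. That is not the cumulative incidence named in the SAP sentence.

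At stake is agreement within the report. The AE curve could end above the percentage in the disposition table. The excess also depends on how much non-AE stopping each arm has, so it need not cancel between arms. The trial is open-label, and Protocol 2.3.1 lists gastrointestinal AEs as a risk of iGlarLixi, so equal stopping patterns in the two arms cannot be taken for granted.

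**Working it through.** **Plan's own figure.** The documents give no expected rate of IMP discontinuation, for AEs or overall. The nearest number is the 10% dropout rate in SAP section 4. There it allows for dropout in the sample size: a two-sample t-test with margin 0.3, SD 1.05, true difference 0, 90% power and two-sided 0.05 needs 259 evaluable per arm. Then 259/0.90 = 287.8, so 288 per arm or 576 in total, against 580 stated. The sample size reproduces. Below, 10% is borrowed only as an assumed level of total IMP discontinuation.

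**Assumed inputs.** F = total proportion stopping IMP; s = share of stops that are for an AE; a = sF (AE stops); o = F − a (other stops).

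**Formulas**, with non-AE stops censored at the time of stopping:

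- Actual cumulative incidence of AE stops: a = sF.
- One minus KM, proportional cause-specific hazards: 1 − (1 − F)^s.
- One minus KM if all AE stops come first: a (no excess).
- One minus KM if all other stops come first: a/(1 − o).

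**Base case**, F = 10%, s = 0.5, so a = o = 5%:

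- Proportional hazards: 1 − 0.90^0.5 = 5.13%, against 5.00%. The excess is 0.13 points, or 0.0013 × 290 ≈ 0.4 of a participant per arm.
- AE stops first: 5.00%.
- Other stops first: 0.05/0.95 = 5.26%.

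**Range over assumed F and s** (proportional hazards):

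| F | s | Cumulative incidence | One minus KM | Excess (points) |
|---|---|---|---|---|
| 5% | 0.50 | 2.50% | 2.53% | 0.03 |
| 10% | 0.25 | 2.50% | 2.60% | 0.10 |
| 10% | 0.50 | 5.00% | 5.13% | 0.13 |
| 10% | 0.75 | 7.50% | 7.60% | 0.10 |
| 20% | 0.50 | 10.00% | 10.56% | 0.56 |
| 30% | 0.50 | 15.00% | 16.33% | 1.33 |

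**Between arms.** Take the same true AE stopping of 5% in both arms, with other stops of 2% in one and 10% in the other. One minus KM gives 1 − 0.93^(5/7) = 5.05% and 1 − 0.85^(1/3) = 5.27%. The apparent gap is 0.22 points where the true gap is zero.

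**Check on discrete data.** With 290 participants, 15 AE stops and 14 other stops in random order (2,000 orderings), one minus KM averaged 5.30% (range 5.22% to 5.40%). Aalen-Johansen gave 5.17% on average, equal to the crude 15/290 = 5.17%.

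**Other ways to handle the unassigned group.** Dropping non-AE stoppers altogether gives 0.05/0.95 = 5.26% in the base case. Keeping them at risk to the end of the treatment period gives 5.00%, the correct value. The SAP says neither.

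**The case against.** The strongest reply is that the SAP never says non-AE stoppers are censored. The overstatement depends on a programming choice, and one possible choice (keeping them at risk to the end) gives the right answer. That stands, so the point is an unassigned group with a conditional consequence. Censoring is still the likely outcome, because it is the usual Kaplan-Meier implementation.

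The second reply is size and role. An excess of 0.13 points compares with a binomial standard error of √(0.05 × 0.95/290) ≈ 1.3 points, about ten times larger. The plot is a disposition display, and SAP 3.6 says of the safety variables: "The analysis of the safety variables will be essentially descriptive, and no testing is planned". This also stands, and it limits the importance of the point. It does not make the curve estimate the quantity in its label.

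Three stronger readings are tempting but not supported:

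- *The curve is always too high once anyone stops for another reason.* It is not: if all AE stops come before all other stops, the two estimates are equal.
- *The secondary safety endpoint is biased.* AEs leading to discontinuation are a secondary safety endpoint, but SAP 3.3 refers their analysis to 3.6.2, where they are reported as number and percentage of participants. Those figures do not depend on Kaplan-Meier.
- *A 10% discontinuation rate is planned.* The 10% is a sample-size dropout rate. Participants who stop IMP are encouraged to stay in the study, so the two rates can differ.

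**Conclusion.** The point holds as a minor improvement. SAP 5.2 names Kaplan-Meier as the estimator and cumulative incidence as the target, and leaves non-AE stoppers without a status in the AE curve. If they are censored, the curve cannot fall below the actual cumulative incidence, and it exceeds it as soon as a non-AE stop precedes a later AE stop.

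At an assumed 10% total discontinuation split equally, the excess is 0.13 points under proportional hazards and 0 to 0.26 points across the possible orders of stopping. It exceeds one point only if total discontinuation is around 30%. The total, the split and the proportional hazards are all assumptions; the documents supply none of them.

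The any-reason curve, the crude AE-discontinuation percentages, the primary and key secondary tests, the type I error and the sample size are not affected.

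**What to change.** In SAP 5.2, specify that the AE curve is the Aalen-Johansen cumulative incidence function. IMP discontinuation for any reason other than an AE is the competing event, and completers are censored at the last dosing date. Keep Kaplan-Meier for discontinuation due to any reason. On the same denominator and the same definition of an AE stop, the AE curve should then end at the crude percentage. A small difference could remain only if some completers are censored before the last stop occurs.

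If the sponsor prefers to keep Kaplan-Meier, the minimum is to state that non-AE stops are censored when they occur and to label the curve as a cause-specific Kaplan-Meier estimate instead of cumulative incidence.

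The cost is about one sentence and a standard software option. The main reason for discontinuation is already tabulated, so no new data are needed.

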5.3 APPENDIX 3 DEMOGRAPHICS AND BASELINE CHARACTERISTICS, PRIOR OR CONCOMITANT MEDICATIONS

Demographics, baseline characteristics, medical surgical history

The following demographics and baseline characteristics, medical and surgical history and diabetes history will be summarized using descriptive statistics in the randomized population.

Demographic and baseline characteristics

- age in years as quantitative variable and in categories (<50, \geq 50 to <65, \geq 65 to <75, \geq 75)
- gender (Male, Female)
- race (Asian)
- baseline body mass index (BMI) in kg/m² as quantitative variable and in categories (<24, \geq 24 to 28, \geq 28)
- randomization stratum of screening HbA1c (<8%, \geq 8%)
- randomization stratum of oral antidiabetic use at screening (Metformin \pm SGLT-2i, Metformin + other OAD)

Baseline efficacy characteristics

- HbA1c % as quantitative variable
- body weight in kg as quantitative variable
- fasting plasma glucose in mmol/L as quantitative variable

- 7-point SMPG in mmol/L as quantitative variable in daily average
- fasting C-peptide level in nmol/L as quantitative variable and by quartiles

Baseline safety will be presented along with the safety summaries.

General medical/surgical history will be collected. Medical and surgical history will be coded to a LLT, PT, HLT, HLGT, and associated primary SOC using the MedDRA version currently in effect at Sanofi at the time of database lock.

Diabetes history

- Duration of type 2 diabetes in years derived as: (Date of informed consent – Date of diagnosis of diabetes + 1)/365.25
- Age at onset of diabetes in years derived as: Year of diagnosis of diabetes – Year of birth
- Duration of prior metformin treatment in years derived as: (Date of informed consent - Date of first intake of metformin + 1)/365.25
- Baseline daily dose metformin in mg as quantitative variable and in categories (<1000, \geq 1000 to <1500, \geq 1500 to <2500, \geq 2500)
- Prior use of SGLT-2i (Yes, No)
- Duration of prior SGLT-2i treatment in years derived as: (Date of informed consent – Date of first intake of SGLT-2i + 1)/365.25
- Prior use of OADs other than metformin or SGLT-2i (Yes, No)
- Duration of prior OADs other than metformin or SGLT-2i in years derived as: (Date of informed consent - Date of first intake of OAD + 1)/365.25
- Gestational diabetes
- Diabetic retinopathy
- Diabetic neuropathy
- Diabetic nephropathy
- Creatinine clearance at baseline in mL/min/1.73m² as quantitative variable and in categories (<30, \geq 30 to < 60, \geq 60 to <90, \geq 90)

In case of partial date of diagnosis of diabetes and date of first intake of metformin/SGLT-2i/other OADs, the date will be imputed only for the derivation of diabetes history as follows:

- If only year is available, it will be imputed as July 1st.
- If year and month are available, it will be imputed to the 15th day.

Prior or concomitant medications

All medications will be coded using the World Health Organization-Drug Dictionary (WHO-DD) using the version currently in effect at Sanofi at the time of database lock.

- Prior medications are those the participant received prior to first injection of IMP. Prior medications can be discontinued before first administration or can be ongoing during treatment period.
- Concomitant medications are any medications received by the participant concomitantly to the IMP during the on-treatment period.
- Post-treatment medications are those the participant received in the period running from the end of the concomitant medications period up to the end of the study.
- A given medication can be classified as a prior medication and/or as a concomitant medication and/or as post-treatment medication. If it cannot be determined whether a given medication was taken prior or concomitantly or post, it will be considered as prior, concomitant, and post-treatment medication.

The prior, concomitant and post-treatment medications will be summarized for the randomized population, by anatomic and therapeutic level. Participants will be counted once in each ATC category (anatomic or therapeutic) linked to the medication.

No imputation of medication start/end dates or time will be performed. A medication with incomplete or missing start date and time and it cannot be determined whether it was taken prior or concomitantly, it will be considered a prior, concomitant, and post-treatment medication.

5.4 APPENDIX 4 DATA HANDLING CONVENTIONS

Analysis windows for HbA1c and body weight

The following analysis windows will be used to decide how the scheduled and/or unscheduled visits will be used in the analyses of efficacy variables: HbA1c and body weight.

A measurement (scheduled or unscheduled, central or local, pre-rescue and premature end of treatment) will be used if it is available and measurement date is within the analysis window.

After applying these time windows, if multiple assessments are associated to the same time point, the closest from the targeted study day will be used. If the difference is a tie, the value after the targeted study day will be used. If multiple valid values exist within a same day, then the first value of the day will be selected.

If there is no measurement for a given parameter in an analysis window, data will be considered missing for the corresponding visit.

The analysis window for HbA1c and body weight is given below.

Table 7 - Analyses window definition for HbA1c and body weight

Scheduled visit post baseline	Targeted study day	Analysis window in study days
Week 4 (Visit 6)	28	1 to 41
Week 8 (Visit 8)	56	42 to 69
Week 12 (Visit 10)	84	70 to 104
Week 18 (Visit 12)	126	105 to 146
Week 24 (Visit 14)	168	≥147

Study days are calculated considering Day 1 as the day of the first injection of open label IMP (or the day of randomization for participant not exposed).

Analysis windows for other endpoints

For safety parameters and efficacy parameters other than HbA1c and body weight, unscheduled, pre-rescue and premature end of treatment assessments will be reallocated to the closest scheduled visit per the schedule of assessment only if the scheduled assessment is missing with the rules defined below:

- Lower bound = targeted day of current scheduled visit - integer part of (targeted day of current scheduled visit – targeted day of the preceding scheduled visit)/2;
- Upper bound = targeted day of current scheduled visit + integer part of (targeted day of the next scheduled visit – targeted day of current scheduled visit -1)/2;
- Lower bound for the first scheduled post-baseline visit is always Day 1 (the day of first IMP injection);
- No upper bound is specified for the last scheduled post-baseline visit.

Unscheduled visits

Unscheduled visit measurements of laboratory data and vital signs will be used for computation of baseline, the last on-treatment value, analysis according to PCSAs, and the shift summaries for safety. They will also be included in the by-visit summaries if they are re-allocated to scheduled visits.

5.5 APPENDIX 5 DEFINITION AND MEDICAL ALGORITHM FOR “RESCUED PARTICIPANTS” / RESCUE MEDICATION USE

Participants who meet one of the following conditions will be considered as “rescued”:

- In the eCRF page “Medications”, if there is any medication with “Rescue Therapy” ticked for “Reason for Treatment”.
- In the eCRF page “Medications”, if there is no medication with “Rescue Therapy” ticked for “Reason for Treatment” and the participant meets any of the criteria in medical algorithm for rescued participants, defined as below.

Medical algorithm for rescued participants

- Short/rapid-acting insulin is given for > 10 days continuously, or ≤ 10 days continuously if it occurs within 2 weeks prior to the last HbA1c measurement.
- New OAD is taken in addition to metformin+/- SGLT-2i (identified from eCRF page “Medications”) > 10 days continuously, or ≤ 10 days continuously if it occurs within 2 weeks prior to the last HbA1c measurement.
- The dose of background therapy is increased for > 10 days continuously, or ≤ 10 days continuously if it occurs within 2 weeks prior to the last HbA1c measurement.

Nevertheless, the participants must not be considered rescued if:

- The date of anti-diabetic initiation is on or after the date of last IMP injection.
- The date of anti-diabetic initiation is before Week 12.
- The anti-diabetic medication was taken due to IMP unavailability during COVID-19 pandemic.

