| HbA1C | X | | | | | X | | X | | X | | X | | X | X | |

| Study period | Screening | Randomization | Study treatment period | | | | | | | | | | | | | Follow-up |
|---|-----------|----------------|------------------------|------|---|------|---|------|----|------|----|------|----|----------------|------------------|-------------|
| Visit number | 1 | 2 ^a | 3 | 4 | 5 | 6 | 7 | 8 | 9 | 10 | 11 | 12 | 13 | 14 | E/D ^d | 15 |
| Visit type (on-site/phone) ^b | site | site | ☎ | site | ☎ | site | ☎ | site | ☎ | site | ☎ | site | ☎ | site | site | ☎ |
| Week ^b | -2 | 0 (Day 1) | 1 | 2 | 3 | 4 | 6 | 8 | 10 | 12 | 15 | 18 | 21 | 24 | E/D | 24 + 3 days |
| FPG ^m | X | X | | | | X | | X | | X | | X | | X | X | |
| Fasting C-peptide ^m | | X | | | | | | | | | | | | X ⁿ | X | |
| Safety laboratory ^k hematology, serum chemistry | X | | | | | X | | X | | X | | X | | X | X | |
| Amylase, lipase, calcitonin | X | | | | | X | | X | | X | | X | | X | X | |
| FSH, estradiol (if necessary to confirm menopausal status) | X | | | | | | | | | | | | | | | |
| Urine pregnancy test ^l (women childbearing potential only) | X | X | | X | | X | | X | | X | | X | | | | |

- a Randomization (V2) can be performed less than 2 weeks after screening visit (V1) if the laboratory data are available.
- b Additional phone calls between visits for titration purposes should be scheduled as often as deemed necessary by the Investigator
- c Visit widows listed in the table are acceptable always using Day 1 (V2) as reference. A visit window of -1 day or +3 days for the post-treatment follow-up visit (V15) is acceptable using the day of V14 as reference. If one visit date is changed, the next visit should take place according to the original schedule.
- d **E/D= Early IMP discontinuation**, participants should have an onsite visit as soon as possible with the assessments (except 7-point SMPG) normally planned at the end of treatment visit (V14). Afterward, the patients should continue in the study up to the scheduled date of study completion. They should be followed up according to the study procedures as specified in the protocol. **In case of rescue therapy**, all assessments (except 7-point SMPG) planned at V14 should be performed before starting rescue therapy, participants then continue the study treatment (including background therapy if appropriate), and all visits and assessments should be performed as scheduled.
- e Systolic and diastolic blood pressure, heart rate.

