- k Safety Laboratory: hematology = WBC, RBC, hemoglobin, hematocrit, platelets, differential blood count (neutrophils, lymphocytes, monocytes, eosinophils, basophils). Serum chemistry = total bilirubin, G-GT, AST, ALT, ALP, creatinine, eGFR, uric acid, sodium, potassium, phosphorus, calcium.

l Urine pregnancy test in female of childbearing potential only will be performed at study sites (local).

m Participants must be in fasting status, not have any food and drinks (except for water) for at least 8 hours.

n Fasting C-peptide sample at Visit 14/Week 24 should be only collected for participants who have C-peptide samples collected at Visit 2/Week0.

AE = adverse event; ALP = alkaline phosphatase; ALT = alanine aminotransferase; AST = aspartate aminotransferase; D = day; ECG = electrocardiogram; eCRF = electronic case report form; eGFR = estimated glomerular filtration rate; FPG = fasting plasma glucose; FSH = follicle stimulating hormone; G-GT = gamma-glutamyl transpeptidase; HbA1c = glycated hemoglobin A1c; IMP = investigational medicinal product; IRT = interactive response technology; RBC = red blood cell; SAE= serious adverse event; SMPG = self-monitored plasma glucose; V = Visit; WBC = white blood cell.

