3.1 APPROPRIATENESS OF MEASUREMENTS

The primary efficacy variable is HbA1c values which reflects the glycemic history of the previous 120 days and is thus an index of mean glycemia, documenting glycemic control over the past 2 to

3 months. HbA1c has also been shown to correlate with the development of long-term complications of diabetes, and reduction of HbA1c is known to reduce the risk of long-term microvascular complications. Therefore, HbA1c is considered an appropriate primary endpoint for assessing the effect of a treatment on glycemic control. In addition to the analysis of the change from baseline in HbA1c, the responder analysis allows the clinical relevance of the reduction observed in HbA1c to be demonstrated. The duration of study treatment is considered to be sufficient for achieving stable conditions with IMP after dose titration and for enabling an adequate assessment of time dependent changes in HbA1c and the concomitant risk of hypoglycemia.

The problem of weight gain in T2DM is widely recognized. Consequently, iatrogenic weight gain is not only unwelcome, but represents an important clinical issue that can become a barrier to the successful management of glycemic control. Body weight control is one of the reasons to choose a GLP-1 RA instead of rapid-acting insulin to intensify basal insulin therapy in this overweight or obese type 2 diabetes population. Taking into account the major impact of insulin-related body weight gain, it is appropriate to include body weight change as secondary efficacy endpoint.

Insulins target primarily, although not exclusively, fasting hyperglycemia, therefore, assessment of fasting glucose is relevant in this study. The 7-point SMPG profiles are also considered as a valuable parameter for monitoring the overall glycemic control throughout the day. β -cell function will be assessed by fasting C-peptide at baseline and Week 24. The glycemic biomarker (HbA1c) will be further evaluated based on the baseline fasting C-peptide levels and therefore to provide evidence that iGlarLixi is effective regardless of baseline β -cell function in patients with T2DM suboptimal controlled with OADs. The effect of iGlarLixi in preservation of β -cell function could also be evaluated via the change in fasting C-peptide from baseline to Week 24 (16).

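### SAP 5.4 does not say which visit grid sets the Week 24 window for fasting C-peptide; on the parameter's own schedule the window opens at Day 1

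*SAP*

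**What the plan says.** SAP 5.4 has two sets of window rules. For two parameters there is a table, Table 7: "The analysis window for HbA1c and body weight is given below". Its Week 24 window is study day 147 or later.

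All other efficacy parameters, fasting C-peptide among them, come under a generic rule. Unscheduled, pre-rescue and premature end-of-treatment values are "reallocated to the closest scheduled visit per the schedule of assessment only if the scheduled assessment is missing". The bounds are midpoints between the current visit and the preceding or next scheduled visit, with two exceptions: "Lower bound for the first scheduled post-baseline visit is always Day 1 (the day of first IMP injection"), and "No upper bound is specified for the last scheduled post-baseline visit".

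Protocol 3.1 says that beta-cell function "will be assessed by fasting C-peptide at baseline and Week 24", and the schedule in Protocol 1.3 has no scheduled C-peptide sample in between. The same schedule marks C-peptide in the early-discontinuation column. Its footnote d says that at early discontinuation "participants should have an onsite visit as soon as possible with the assessments (except 7-point SMPG) normally planned at the end of treatment visit", and it asks for the Visit 14 assessments (again without 7-point SMPG) before rescue starts.

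The analysis (SAP Table 2 and 3.3.2.2) is a treatment-policy comparison at Week 24. Missing values are handled by the same pattern-based multiple imputation as the primary endpoint.

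**The concern.** The generic rule speaks of preceding and first post-baseline visits but does not say whose visits these are. For a parameter sampled at most visits this hardly matters. For C-peptide it decides the result, because Week 24 is both the first and the last scheduled post-baseline sample. On the parameter's own schedule the Day 1 provision and the open upper end then apply to one and the same visit, and the window covers the whole trial.

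A sample drawn soon after stopping study treatment, or just before rescue begins, would then be analysed as a measured Week 24 value whenever the true Week 24 sample is missing. It does not show the participant's state at Week 24 after the intercurrent event, which is what a treatment-policy estimand asks for. It would also replace the imputation that the SAP prescribes for exactly those participants. Two programmers could follow the text faithfully and build different datasets.

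**Working it through.** **Inputs.** Target days 28, 56, 84, 126 and 168 (SAP Table 7). Bounds for target T (SAP 5.4): lower = T − int((T − previous)/2); upper = T + int((next − T − 1)/2); first lower bound = Day 1; last upper bound open. Visit schedule from Protocol 1.3; earliest rescue alert at Week 12 (Protocol 6.8.4), about Day 84.

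**Step 1: reproduce Table 7 with the generic formula.**

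| Visit | Lower | Upper | Table 7 |
|---|---|---|---|
| Week 4 | 1 | 28 + int(27/2) = 41 | 1 to 41 |
| Week 8 | 56 − int(28/2) = 42 | 56 + int(27/2) = 69 | 42 to 69 |
| Week 12 | 84 − int(28/2) = 70 | 84 + int(41/2) = 104 | 70 to 104 |
| Week 18 | 126 − int(42/2) = 105 | 126 + int(41/2) = 146 | 105 to 146 |
| Week 24 | 168 − int(42/2) = 147 | open | 147 or later |

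All five rows match, so the formula is being read as the SAP intends.

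**Step 2: apply it to C-peptide (target Day 168).**

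- Own schedule: the visit is first and last, so the window is Day 1 with no upper bound. Without the Day 1 provision it would start at 168 − int((168 − 1)/2) = 85.
- Common grid of on-site visits (preceding visit Week 18): 168 − int((168 − 126)/2) = 147.
- Common grid of all visits (preceding visit the Week 21 call, Day 147): 168 − int((168 − 147)/2) = 158.

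The lower bound is therefore Day 1, 147 or 158, depending on a choice that the SAP does not state.

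**Step 3: one visit, two parameters, own-schedule reading, Week 24 samples missing.**

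- Discontinuation visit on Day 28: HbA1c is a Week 4 value and Week 24 HbA1c stays missing. C-peptide becomes Week 24, 168 − 28 = 140 days before target.
- Pre-rescue visit at about Day 84: HbA1c falls in the Week 12 window. C-peptide becomes Week 24, 168 − 84 = 84 days before target.

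**Step 4: other efficacy endpoints.** FPG is also measured at Week 18, so its own schedule gives 168 − int(42/2) = 147. For 7-point SMPG (Weeks 12 and 24) the bound is 168 − int(84/2) = 126, but Protocol 8.1.3.2 does not require a profile at discontinuation or pre-rescue visits, so no such profile is planned. C-peptide is the exposed endpoint.

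**Step 5: size.** If k of n participants in an arm have a moved value, the arm's mean change shifts by (k/n) × (mean early-sample change − mean imputed change). The documents give neither k nor the difference. As an assumption, with n = 290: 5/290 = 1.7%, 15/290 = 5.2%, 29/290 = 10%. The 29 is the 10% planning dropout rate and not a ceiling. These are weights, not biases. The n may be below 290, because "Fasting C-peptide sample at Visit 14/Week 24 should be only collected for participants who have C-peptide samples collected at Visit 2/Week0".

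**The case against.** The best case against runs as follows.

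- **The text can be read as a common grid.** The rule speaks of the closest scheduled visit. On the overall visit grid the closest visit to Day 28 is Week 4, where no C-peptide is scheduled and nothing is missing to be filled. Table 7 also puts two parameters on one grid and has no Week 2 row, although body weight is measured at Week 2. This stands: the common-grid reading is not excluded, and it removes most of the harm. It does not settle the matter, because the condition for moving a value is that the parameter's own scheduled assessment is missing, and the Day 1 provision is worded as holding always.
- **Few participants should be affected.** After discontinuation, "Afterward, the patients should continue in the study up to the scheduled date of study completion". Rescued participants also keep their visits, and a true Week 24 sample takes precedence. This stands, and it limits k.
- **Using the early sample may be intended.** It is a scheduled measurement, and the SAP uses all assessments regardless of intercurrent events. An imputed value is not shown to be less biased. That is fair, but if the sponsor wants the discontinuation sample to serve as the endpoint, the SAP should say so, because this differs from the imputation it prescribes.

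A reader might also infer that moved samples would count as retrieved dropouts, and so towards the minimum of 10 per arm in SAP 3.2.2. The documents do not support this. That section counts observed Week 24 data after discontinuation and does not say whether a moved sample qualifies.

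**Conclusion.** The point holds as an unresolved rule with one unfavourable reading, and it is minor. SAP 5.4 does cover C-peptide, through the generic rule; what it leaves open is the visit grid. On the parameter's own schedule the Week 24 window is Day 1 onward, and early samples displace the planned imputation. On a common grid the window starts at Day 147 or 158.

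Two stronger conclusions are tempting. One is that the SAP definitely carries early C-peptide values forward; it does so on one of two open readings only. The other is that the treatment comparison is biased towards one arm; the number affected, and the size and direction of any bias, cannot be derived. Primary and key secondary results are not touched: HbA1c and body weight have Table 7, and C-peptide lies outside the gate-keeping procedure (SAP 3.5).

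**What to change.** State in SAP 5.4 that the Week 24 window for fasting C-peptide is study day 147 or later, as in Table 7. Where only earlier discontinuation or pre-rescue samples exist, treat Week 24 as missing under the planned imputation and do not treat those samples as observed Week 24 data. List them separately and, if wanted, use them in a sensitivity analysis.

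This takes one or two lines and no new data. A few measured early values would be replaced by imputed ones. The confidence interval would be slightly wider, and the return-to-baseline fallback somewhat likelier for C-peptide. Day 147 is not the only defensible bound, but it treats C-peptide and HbA1c from the same visit alike.
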